18. DATA HANDLING AND RECORDKEEPING

An overview of study data handling and recordkeeping procedures and restrictions is provided in the subsequent sections; please refer to the CSA for further details.

18.1. Data Capture

As stated in [Section 16.1](#), this study will use eCRFs for capturing data. All entries, corrections, and alterations will be made by the Investigator or other authorized study personnel. All data entries will be verified for accuracy and correctness by independent monitors. The electronic data capture system maintains a full audit trail.

Adverse events will be coded using MedDRA. Concomitant medications will be categorized using the WHO-Anatomical Therapeutic Chemical classification system.

18.2. Inspection of Records

Alkermes or its representative will be allowed to conduct site visits to the investigational facilities for the purpose of monitoring any aspect of the study. The Investigator agrees to allow the Monitor to inspect the drug storage area, study drug stocks, drug accountability records, subject charts and source documents, and other records relative to study conduct.

18.3. Retention of Records

Retention and storage of all essential clinical study documents shall be governed by the terms and conditions of the site's CSA and in accordance with ICH Guidelines/local regulatory requirements as follows:

Essential documents should be retained until at least 2 years after the last approval of a marketing application in an ICH region and until there are no pending or contemplated marketing applications in an ICH region, or until at least 2 years have elapsed since the formal discontinuation of clinical development of the investigational product. These documents should be retained for a longer period, however, if required by the applicable regulatory requirements or by the terms of the CSA. It is the responsibility of the Sponsor to inform the Investigator/institution as to when these documents no longer need to be retained.

Subjects' medical files should be retained in accordance with the applicable legislation and in accordance with the maximum period of time permitted by the hospital, institution, or private practice.

18.4. Use of Information and Publication Policy

Data generated in this study are proprietary information that are the sole property of Alkermes. Results of the study are to be held in confidence by both the investigators and the Sponsor.

Please refer to the CSA for details on the procedures for publishing and presenting data.

- Submit this form completed to PPD [redacted] for any ALK5461-217 subject who completed Visit 13 (End of Treatment) ≥ 30 days from planned screening date
- Investigator is encouraged to call the Medical Monitor to discuss each case in advance of dosing in ALK5461-218 as needed
- Ensure the fully executed form is obtained prior to scheduling Visit 1

Key Criteria	Is item applicable to this subject?	Comments
GENERAL INFORMATION:		
Subject participated or is participating in another clinical trial since completion of ALK5461-217	 Yes  No	If yes, provide details:
Changes in contraceptive method since completion of ALK5461-217	 Yes  No	If yes, provide details of new/planned contraceptive method:
For females, is the subject pregnant or planning to become pregnant	 Yes  No	

ANTIDEPRESSANT THERAPY (ADT) ASSESSMENT:		
Confirm ADT details for the subject	Current ADT: Dose: Frequency: Start Date:	
Please detail any changes and/or interruptions of the subject's ADT since completion of ALK5461-217 including root causes or confirm there have been no changes. If the subject has changed his or her ADT, please provide detail on his or her level of improvement and clinical judgment regarding initiating augmentation therapy:		
MEDICAL AND PSYCHIATRIC HISTORY ASSESSMENT:		
Has the subject attempted suicide or has the perceived risk of suicide increased since completion of the ALK5461-217 study?	 Yes  No	If yes, provide details:
Have there been any significant changes to Medical History, Psychiatric History or Concomitant Medications, e.g. - Newly identified or emergent allergies - Substance abuse (disclosed or suspected by PI) - New psychiatric diagnoses - Hospitalization for psychiatric reasons - Initiation of ECT therapy - New medication(s) initiated - Medications discontinued	 Yes  No	

If yes, please complete the table below to detail all changes:

Medical/Psychiatric History Term (please use DSM-5 terminology for psychiatric diagnoses)	Onset Date	End Date/ Ongoing	Associated Medications	Concomitant Treatment Include non-pharmacological therapies	Dose/ Freq	Start Date	Stop Date / Ongoing	Requires Washout?	Washout completion date (if applicable)
			 Y  N					 Y  N	
			 Y  N					 Y  N	
			 Y  N					 Y  N	
			 Y  N					 Y  N	
			 Y  N					 Y  N	
			 Y  N					 Y  N	
			 Y  N					 Y  N	
			 Y  N					 Y  N	

OTHER OBSERVATIONS:	
Other concerns/information?	 Yes  No
Please provide detail:	

Principal Investigator

Note: If the third option below is selected, you will not receive an acknowledgment (i.e. full execution of this form from PPD)

I attest that no changes have occurred with the subject
 I attest that there are new findings, however in my view these changes would NOT compromise safety when dosed in ALK5461-218
 I attest there are new findings that in my view would compromise the safety of the subject if dosed in ALK5461-218

 PI Name Signature Date

PPD Medical Director

I acknowledge the Principal Investigators' attestation based on information provided by the site on this form.

 Reviewer's Name Signature Date

21. APPENDIX B: PARTIAL LIST OF PROHIBITED CYTOCHROME P450 (CYP) 3A4 INHIBITORS AND INDUCERS

A list of CYP3A4 inhibitors and inducers that subjects are to avoid is presented in Table 5 below. This list is not comprehensive.

Table 5: Partial List of Cytochrome P450 (CYP) 3A4 Inhibitors and Inducers

Moderate-to-Strong Inhibitors		Moderate-to-Strong Inducers
Aprepitant	Imatinib	Bosentan
Boceprevir	Ketoconazole	Carbamazepine
Ciprofloxacin	Lopinavir/Ritonavir	Efavirenz
Clarithromycin	Nefazodone	Enzalutamide
Conivaptan	Nelfinavir	Etravirine
Crizotinib	Posaconazole	Modafinil
Danoprevir/Ritonavir	Ritonavir	Phenobarbital
Diltiazem	Saquinavir/Ritonavir	Phenytoin
Erythromycin	Telaprevir	Rifampin
Fluconazole	Troleandomycin	Rifabutin
Indinavir/Ritonavir	Verapamil	St. John's Wort
Itraconazole	Voriconazole	

Source: ([Food and Drug Administration, 2016](#)).

1. INTRODUCTION

This statistical analysis plan (SAP) describes the statistical methods and data presentation to be used at study completion for analyzing and reporting ALKS 5461 data for Study ALK5461-218, A Phase 3b Extension Study of Adjunctive ALKS 5461 in the Treatment of Refractory Major Depressive Disorder (MDD). This document has been prepared based on Alkermes ALK5461-218 study protocol v3.0 (dated 19 November 2019) [1].

1.1. Study Objectives

The objective of this study is to evaluate the long-term safety and tolerability of adjunctive ALKS 5461 in adults who have treatment-refractory MDD.

1.2. Summary of the Study Design and Schedule of Assessments

This is an open-label, Phase 3b, multicenter extension study to evaluate the long-term safety and tolerability of ALKS 5461 administration for use as an adjunctive therapy to antidepressants for the treatment of refractory MDD. Subjects who complete participation in the ALK5461-217 study will be eligible for enrollment into the study.

At Visit 1 (day 1), all eligible, consenting subjects will begin the treatment period. One tablet will be taken sublingual on each dosing day. From Day 1 onward, all participating subjects will take ALKS 5461 2/2 mg and an approved antidepressant therapy (ADT).

Study staff will administer the first dose of ALKS 5461 on Day 1. From that point on during the treatment period, the staff will dispense ALKS 5461 for subjects' self-administration. Subjects will be advised to take the study drug at bedtime.

During the treatment period, subjects will return to the clinic for periodic scheduled visits, at which time safety and tolerability will be assessed, as well as a 2-week post-discontinuation Follow-up visit.

For a missed visit, the study site should attempt to contact the subject to reschedule. Subjects who discontinue from the study prematurely will be encouraged to return for an Early Termination visit and a 2-week post-discontinuation Follow-up visit.

Subjects' demographic data will be carried over from the ALK5461-217 study. If ≥ 30 days have elapsed since end-of-treatment in ALK5461-217, medical and psychiatric history for the intervening period will be queried and updated in the ALK5461-218 database as necessary.

[figure not shown]
At each visit, subjects will be asked about the medications they have taken since the last visit.

Drug adherence for ALKS 5461 will be reviewed with subjects at each visit.

Please refer to the protocol for a detailed schedule of assessments. A brief schematic of study design is provided in Figure 1. A summary of the schedule of safety assessments is presented in

Table 1.

Figure 1: Study Design Schematic

Abbreviations: EOS=end of study; EOT=end of treatment; ET=early termination

Table 1: Schedule of Safety Assessments

Procedure or Assessment	Schedule
Dispensation of study drug	All scheduled visits prior to End of Treatment or Early Termination Visit (i.e., Screening [Day 1], weeks 1, 2, 6, 12, 20, 28, 36, 44, 52, 60)

 Adverse Event C-SSRS (since last visit) Drug Adherence Concomitant Medications Urine Pregnancy Test 	Screening (Day 1), weeks 1, 2, 6, 12, 20, 28, 36, 44, 52, 60, 68 (ET/EOT), 14 days after last dose (Follow-up visit)
Urine Drug Screen	Screening (Day 1), at subsequent visits as needed based on the investigator's judgment

Abbreviations: C-SSRS=Columbia-Suicide Severity Rating Scale; EOT=end of treatment; ET=early termination

1.3. Criteria for Evaluation

Safety and Tolerability:

The following assessments will be collected to measure safety and tolerability throughout the study:

- Adverse events (AEs)
- Serious adverse events (SAEs)
- Columbia Suicide Severity Rating Scale (C-SSRS)

2. SAMPLE SIZE CONSIDERATION

No formal sample size calculation has been performed. A sample size of up to 250 subjects is based on an estimated number of subjects who may wish to continue from Study ALK5461-217.

3. DATA ANALYSIS

3.1. General Statistical Methodology

Summary statistics (n, mean, standard deviation [SD], median, minimum, and maximum for continuous variables, and number and percentage of subjects in each category for categorical variables) will be provided for subjects receiving one or more doses on ALKS 5461. Summary statistics will be based on observed data. In general, only data collected during the ALK5461-218 study will be summarized even though baseline demographic data may have been assessed in study ALK5461-217.

Source data for the summary tables will be presented as subject data listings.

3.2. Study Population

3.2.1. Definitions of Analysis Populations

Safety Population will consist of all enrolled subjects who received at least 1 dose of study drug in the ALK5461-218 study.

Post-discontinuation Safety Population will consist of subjects who received at least 1 dose of study drug in the ALK5461-218 study, and met one of the following criteria:

- Subjects who entered the Post-discontinuation Period and had a Post-discontinuation Follow-up Visit
- Subjects who did not enter the Post-discontinuation Period (i.e., final visit was last visit in treatment period), but had at least 1 PDEAE reported
- Subjects who died after either completing the treatment or having an Early Termination (ET) Visit

3.2.2. Definitions of Baseline and Analysis Periods

Baseline

For demographics and baseline disease characteristics, baseline will be defined as assessments recorded at Visit 1. Note that the actual assessment for some variables was made in the antecedent study, ALK5461-217. For adverse events, baseline will be defined as prior to Visit 1 (i.e., the period from completion of ALK5461-217 to first dose received in ALK5461-218). For the Columbia-Suicide Severity Rating Scale (C-SSRS) baseline will be defined as the assessment made during Visit 1.

Treatment Period

The treatment exposure period (i.e., Treatment Period) will be defined as the interval between Visit 1 and the last dose date plus 1 day, inclusive.

Visit 1 is the first scheduled visit during the scheduled treatment period and Visit 12 is the last scheduled visit including ET visit during treatment.

Post-Discontinuation Period

Post-discontinuation Safety Period will be defined as the interval starting from the last dose date plus 2 days to the end of study date, inclusive.

3.2.3. Disposition

Subject disposition will be summarized for all subjects. The number and percentage of subjects will be summarized for the following:

- Subjects who enrolled in the study
- Subjects in the Safety Population
- Subject who completed treatment (as indicated on the case report form (CRF))
- Subjects who completed the study (as indicated on the CRF)
- Subjects who discontinued from the study

For subjects who prematurely discontinue from the study, the reasons for discontinuation as recorded on the disposition CRF will be presented. Percentage will be calculated based on Safety Population.

A listing of disposition for all subjects will be provided.

3.2.4. Protocol Deviations

Subjects with major protocol deviations will be summarized along with supportive listings for each of the following categories:

- Did not meet the inclusion / exclusion criteria
- Received prohibited medications
- Dosing error
- Other major protocol deviation

3.3. Demographic Characteristics

Demographic characteristics data (i.e., age, gender, primary race, ethnicity and region (United States [US], non-US)) will be summarized for the Safety Population. Categories for missing data will be provided as necessary.

Medical history collected since the completion of the antecedent study will be summarized using the number of observations and percentage of subjects reporting each category for the Safety Population.

Demographic and baseline listings will be provided for all subjects.

3.4. Prior and Concomitant Medications

Prior medications are defined as medications taken between the completion of study ALK5461-217 and the first dose of ALKS 5461 in this study. Concomitant medications are defined as medications taken during the treatment period (defined as first dose date and the last dose date of study drug plus 1 day, inclusive). All medications as documented by the investigator will be coded using the WHODrug Format C, Version March 2017, WHO DDE + Herbal.

Prior medications and concomitant medications will be summarized by Preferred Term (PT) for the Safety Population. For the summary tables, if a subject has taken a prior or concomitant medication more than once, the subject will be counted only once for the medication.

Listings will be provided for all prior and concomitant medications.

3.5. Treatment Adherence Rate and Extent of Exposure

Treatment adherence to the daily dosing schedule of study drug is measured as the rate of actual compared to intended number of doses to be taken during the ALK5461-218 study. Percentage of treatment adherence will be calculated during the treatment period for the Safety Population as follows:

$$100 \times \frac{\text{Total tablets taken}}{\text{Total tablets subject should have taken from the first dose date to the last dose date, inclusive}}$$

Duration of exposure to study drug is defined as the number of days from the first dose date of study drug taken to the date of the last dose taken during the ALK5461-218 study, inclusive.

Treatment adherence and exposure of study drug will be summarized for the Safety Population. Treatment adherence will be summarized as a continuous measure and as a categorical measure for each adherence rate category (rounded to the whole number): <70%; ≥70% to 80%; >80% to 90%; >90% to 100%; >100% to 110%; >110% to 120%; and >120%.

The number of subjects exposed to study drug and the extent of exposure (i.e., days of treatment) will be summarized as a continuous measure using descriptive statistics.

3.6. Safety Analysis

3.6.1. General Considerations

All safety endpoints will be summarized based on observed data for the Safety Population during the Treatment Period / during the Post-discontinuation Safety Period.

3.6.2. Adverse Events

Adverse events will be coded by System Organ Class (SOC) and Preferred Term using the Medical Dictionary for Regulatory Activities (MedDRA, version 20.0). The verbatim term will be included in the AE listings.

An AE will be considered as a treatment-emergent adverse event (TEAE) if it starts or worsens (if present during baseline period) on or after first dose date during the treatment period (defined as the period between the first dose date and last dose date +1). An AE will be considered as a PDEAE if it starts during the Post-discontinuation Safety Period (defined as after the period after last dose date plus 2 days, inclusive, and include AEs with preferred terms that may have also

been TEAEs during the Treatment Period. For the determination of TEAEs during the treatment period, AEs with the greatest severity before the baseline will be used as the benchmark for the comparison of the AEs occurring during the treatment period. For PDEAEs, all AEs starting during the Post-discontinuation Safety Period will be summarized.

All AEs will be listed by subject. TEAEs / PDEAEs, deaths, serious adverse events (SAEs), and AEs leading to study discontinuation will be included in the summary tables. For AEs leading to study discontinuation or deaths, the AEs will be summarized in the period in which the discontinuation or death occurred. Drug-related TEAEs include those scored as definitely related, probably related, and possibly related by the investigator.

The following summary tables will be produced for the treatment period / Post-discontinuation Safety Period for the Safety Population:

- Overview AE summary tables (TEAEs / PDEAEs)
- TEAEs / PDEAEs by System Organ Class and Preferred Term
- TEAEs / PDEAEs by Preferred Term
- TEAEs / PDEAEs experienced by $\geq 5\%$ of subjects by Preferred Term
- TEAEs / PDEAEs by System Organ Class, Preferred Term, and Severity
- Drug-related TEAEs by Preferred Term
- SAEs (fatal and non-fatal) by Preferred Term
- AEs leading to study discontinuation by System Organ Class and Preferred Term
- AEs leading to study discontinuation by Preferred Term

A subject having the same AE (as determined by the coded MedDRA preferred term) more than once will be counted only once in the calculation of the number and percentage of subjects for that AE. Similarly, if a subject has more than one AE in a System Organ Class, the subject will be counted only once in the number of subjects with an AE for that System Organ Class. If a subject has the same AE on multiple occasions, the highest severity (severe > moderate > mild) recorded for the event will be presented in the AE by severity summary. Similarly, if a subject has the same AE on multiple occasions, the closest relationship (related > not related, where related includes definitely related, probably related, and possibly related; and not related includes probably not related and definitely not related) recorded for the event will be presented in the AE by relationship summary.

Subgroup analyses are planned for TEAEs only. Subgroups to include:

- Demographics (age [<55 years, ≥ 55 years], race [white, all other races], gender [female, male])
- Region (US, non-US)

Subject listings for AEs will be included.

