13.1. Definition of Adverse Event

An AE is any untoward medical occurrence in a patient or clinical investigation subject who has been administered a pharmaceutical product. The occurrence, which may or may not have a causal relationship with the investigational treatment, may include any clinical or laboratory change that does not commonly occur in that subject and is considered clinically significant.

Illnesses present prior to the subject signing the informed consent form (ICF) are considered to be preexisting conditions and are documented on the medical history eCRF. Preexisting conditions that worsen during the study are entered on the AE eCRF.

Pregnancy is not considered an AE although a subject will be withdrawn from the study if a pregnancy occurs. As described in [Section 8.4.1](#), the pregnancy, including a partner's pregnancy, must be reported to Alkermes, and additional follow-up may be required.

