14.7. Safety and Tolerability Analyses

All safety assessments will be summarized using descriptive statistics. Reported AE terms will be coded using the Medical Dictionary for Regulatory Activities (MedDRA).

Treatment-emergent AEs (TEAEs) will be defined as AEs that occur or worsen after the first dose of study drug. The incidence of TEAEs will be summarized by System Organ Classes and

Preferred Terms and by severity and relationship to study drug. Subjects with SAEs and AEs leading to discontinuation from the study will be summarized. The number and percentage of subjects with C-SSRS assessments at post-baseline will be summarized. Concomitant medications will be categorized using the World Health Organization (WHO) Anatomical Therapeutic Chemical (ATC) classification system. Listings will be provided for all concomitant medications.

Further details will be described in the Statistical Analysis Plan.

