5. CHANGES IN CONDUCT OR PLANNED ANALYSES FROM THE PROTOCOL

Not applicable.

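### The SAP defines post-discontinuation AEs by start date only, so an AE ongoing at the last dose that worsens after withdrawal need not be counted as a post-discontinuation event

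*SAP*

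**What the plan says.** SAP 3.2.2 divides follow-up into two adjoining periods. The Treatment Period runs from Visit 1 to last dose + 1 day, and the Post-discontinuation Safety Period from last dose + 2 days to the end of study.

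SAP 3.6.2 applies different tests in the two periods:

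- **TEAE:** an AE qualifies "if it starts or worsens (if present during baseline period) on or after first dose date during the treatment period". The benchmark is the greatest severity before baseline.
- **PDEAE:** "An AE will be considered as a PDEAE if it starts during the Post-discontinuation Safety Period". The same section repeats the rule: "For PDEAEs, all AEs starting during the Post-discontinuation Safety Period will be summarized". No severity benchmark is given. The section does say that PDEAEs include preferred terms that may also have "been TEAEs during the Treatment Period".
- **Severity table:** where a subject has the same AE more than once, "the highest severity (severe > moderate > mild) recorded for the event will be presented in the AE by severity summary".

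Protocol 14.7 has a single definition and no second period: "Treatment-emergent AEs (TEAEs) will be defined as AEs that occur or worsen after the first dose of study drug". Protocol 13.1 places illnesses present before consent in the medical history and adds: "Preexisting conditions that worsen during the study are entered on the AE eCRF". SAP 5, which is the place for changes from the protocol, reads "Not applicable".

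**The concern.** The protocol synopsis makes the 2-week period after stopping part of the safety evaluation. In that period the evidence consists of AEs, SAEs and the C-SSRS (Protocol 13). Protocol 11 plans no formal efficacy assessment, and the schedule in Protocol Table 3 contains no depression or withdrawal scale. The PDEAE tables are therefore the main summary of what happens, other than suicidality, once the drug is removed.

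A definition that recognises only new starts can miss a problem that was already present and became worse on withdrawal. Two distortions are possible. The post-discontinuation tables can be too low, and the on-treatment severity table can carry a severity that was reached only after the drug had stopped. There is also a small knock-on effect. Under SAP 3.2.1, a subject with no follow-up visit can enter the Post-discontinuation Safety Population by having a PDEAE, and a subject whose only event was a worsening would not qualify by that route.

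**Working it through.** The plan gives no figure to reproduce, so the check is date logic. Let L be the last dose date and Day 1 the first dose date.

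**Rules, from SAP 3.2.2 and 3.6.2**

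- TEAE if Day 1 ≤ start ≤ L+1, or if the AE was present in the baseline period and Day 1 ≤ date of worsening ≤ L+1.
- PDEAE if start ≥ L+2, up to the end of study.

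The periods meet without gap or overlap: L+1 is treatment and L+2 is post-discontinuation. With the follow-up visit at 14 (±4) days after the final dose (Protocol Table 3), the planned post-discontinuation window is 14 − 2 + 1 = 13 days, with a range of 10 − 2 + 1 = 9 to 18 − 2 + 1 = 17 days.

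**Classification of a worsening at L+5**

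| Case | How it is recorded | TEAE | PDEAE |
|---|---|---|---|
| a | AE began on drug, kept as one record | Yes | No |
| b | AE began on drug, second record opened at L+5 | First record | Second record |
| c | AE recorded before the first dose, kept as one record | No | No |
| d | MDD in medical history, AE entered with onset L+5 | No | Yes |
| e | MDD in medical history, AE entered with the illness's original onset date | No | No |

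**Reading the table**

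- Case a is the clear failure. The subject already counts as having the TEAE, so the event is not lost from the study. What is lost is its appearance as a post-discontinuation event. If the site raises the severity on that record, a single severity value cannot be divided between periods, and the later value goes into the TEAE severity table.
- Cases c and e appear in neither set of tables. Protocol 14.7 would count both, because the worsening falls after the first dose and the definition has no end date. This is where the SAP is narrower than the protocol.
- Case c should be rare. AE collection begins at consent (Protocol 13.4), and consent and the first dose both take place at Visit 1 (Protocol 8.1 and Table 3).
- Cases b and d are counted correctly. They differ from a and e only in how the record is opened and dated.

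Neither document says whether an increase in severity opens a new AE record, or what start date a worsened pre-existing condition receives. Protocol 13.4 requires an intensity rating and follow-up of each AE but does not settle either question.

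**The case against.** A reader might infer that relapse of depression after stopping is absent from the tables, and that every subject is exposed to this because every subject has MDD. The documents do not support that. Under Protocol 13.1 stable MDD is medical history and not an open AE. When it worsens after the last dose, the AE record is created at that point, and dating it at the worsening is the natural reading. It then starts in the post-discontinuation period and counts as a PDEAE (case d). No section tells sites to backdate it.

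Other provisions also limit the loss:

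- The clause on shared preferred terms admits a repeat event when a new record is opened.
- The severity rule concerns the same AE on several occasions, and the tables are produced separately by period. Post-withdrawal severity reaches the TEAE table only when one record spans both periods and its severity is updated.
- All AEs are listed. Deaths and AEs leading to discontinuation are assigned to the period of the outcome. Post-discontinuation C-SSRS values are summarised (SAP 3.6.3). Hospitalisation for worsening behavioural health is an SAE (Protocol 13.2).
- The eCRF completion instructions are not in the protocol or SAP, and the SAP places the dataset and programming specifications and mock tables in separate documents. The recording convention is unknown, not shown to be wrong.
- The study is single-arm and descriptive.

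These points stand, and they remove any claim of systematic loss of depressive relapse. They do not remove case a. The shared-term clause does nothing for an AE kept as one record, listings do not give incidence, the outcome-date rule does not extend to worsening, and the C-SSRS covers suicidality and self-injury only.

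**Conclusion.** The point holds in limited form. The PDEAE definition has no worsening limb, although the SAP's own TEAE rule and Protocol 14.7 both have one, and SAP 5 records no change. An AE ongoing at the last dose and kept as one record, which worsens from last dose + 2 days, is not counted as a PDEAE. If its severity field is updated, that severity can be shown as on-treatment.

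This rests on two assumptions about recording: that an open AE may be carried as a single record through the last dose and, for the severity table, that its severity may be updated. For pre-existing MDD the loss requires the further assumption that the AE is dated to the original onset. The documents neither confirm nor exclude these practices, and they give no rate of worsening after withdrawal, so the size of the effect cannot be stated. The change is still worth making, because the rule is explicit, stated twice, and governs the main summary of a short window of about two weeks in which little else is measured.

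**What to change.** 1. In SAP 3.6.2, define a PDEAE as an AE that starts during the Post-discontinuation Safety Period, or that worsens in that period relative to the greatest severity recorded up to last dose + 1 day.
2. In the severity tables, use only the severity reached in the period being tabulated.
3. Confirm from the eCRF completion instructions, or instruct sites, that a severity increase after the last dose, including worsening of a pre-existing condition, is recorded as an AE dated at the worsening. Items 1 and 2 need this, because they cannot be programmed without dated severity changes.
4. If the start-only rule is kept, state it in SAP 5 as a departure from Protocol 14.7.

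The cost is small: a sentence or two in the SAP, one recording instruction and minor programming. PDEAE counts will be slightly higher. Timing is the main drawback. The SAP is based on the protocol version of 19 November 2019, and the protocol estimates last completion in Q1 2020. If the instruction is introduced late, subjects who have already finished follow-up may have been recorded under a different convention, and the report should say so.
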